A recent Cochrane review found that BUP-300 mitigates the magnitude of weight gain relative to PLA and varenicline, though effects were modest and not robust at long-term follow-up.⁹⁷ Bupropion may facilitate weight loss by suppressing appetite, decreasing food reward,⁹⁸ and increasing metabolic rate via action on mesolimbic dopamine and hypothalamic melanocortin systems.⁹⁹ One of the first large trials tested the dose dependency of BUP for weight loss and showed that 400 mg/day outperformed 300 mg/day.¹⁶ Doses \geq 400mg BUP has since been the primary dose studied for weight loss, with results supporting the efficacy of BUP (vs. PLA) in various studies (2%–10% of initial body weight),^{16,17,100-103} including trials in depressed patients.¹⁰³ High dose bupropion recently garnered FDA approval for weight loss when combined with naltrexone. Because the efficacy of BUP is not dependent on a diet/behavioral weight loss intervention platform,^{16,17,100-103} **BUP-450 could prevent weight gain the smoking cessation context without weight loss counseling.** Thus, high dose bupropion may prevent post-cessation weight gain better than other cessation treatments, particularly among the population of anhedonic smokers for which weight-related health consequences are of particular concern.

A.11 Summary of the Significance of the Proposed Study

The proposed RCT of BUP-450 vs. BUP-300 aims to identify a viable method of offsetting tobacco-related health disparities facing SWPS and two other leading causes of morbidity and mortality—mental illness and excessive weight. Results will be readily translatable to real-world clinics, given the modest cost of BUP-450 and the existing prescribing practices of high dose BUP for weight loss and psychopathology. If BUP-450 does not outperform BUP-300 in quit outcomes but improves weight gain and/or mental health without additional side effects, the trial would still provide invaluable evidence of a new cessation treatment that is equally efficacious to a front line treatment (i.e., BUP-300) but has superior metabolic and/or mental health benefits.

B. INNOVATION

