Week = from quit day (0). Ax = Assessment. F/U = follow-up. R = Randomization. Tx = *Visit by can be by phone. **Additional baseline measures (see C.6). ***Body adiposity scan

Medication. Formulation. Bupropion XL 150mg, and placebo tablets matching in appearance (Rejuvination Labs, San Diego, CA) will be used. **Regimen.** The selected regimen was based on medication guidelines¹⁸¹ and evidence that a 4-week extended run-in prior to quit day produces superior outcomes relative to the standard 1-week run-in,⁷⁰ All dosing is once per day per XL formulation guidelines.¹⁸² BUP-450 involves a 17-day up-titration (1 x 150 mg tablet for 3 days followed by 2 x 150 mg tablet for 14 days), 10-day pre-quit run-in (3 x 150 mg tablets), 8-week post-quit treatment period (3 x 150 mg tablets), and 1-week down-titration (2 x 150 mg tablet). The BUP-300 regimen is identical except that pre-quit run-in and 8-week post-quit treatment period involves 1 x placebo + 2 x 150mg to match number of tables taken across conditions and differentiate dose. **Clinical monitoring/safety:** In addition to eligibility screen, participants will meet with the physician at: (a) treatment outset to review the medication, managing and/or reporting side effects, pregnancy contraindications, and rationale for taking the medication for ≥ 4

weeks prior to quitting; and (b) end of treatment to review treatment, collect labs, and discuss down-titration. All participants will be given a 24-hour phone number and physician office hours will be available as needed. Vital signs, weight, and side effects, including suicidal ideation, will be monitored at each study visit. In the event that significant medical problems are encountered, the blind will be broken and appropriate medical treatment will be provided.

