Outcome assessments (Baseline, 4-wk, 8-wk, 16-wk, 26-wk). Primary outcome: Point prevalence abstinence (PPA) self-report of no smoking or use of any other tobacco products (including e-cigarettes) in past 7-days (not even a puff) verified by salivary cotinine ≤ 10 ng/ml is our primary outcome. Secondary outcomes: (a) Smoking cessation milestones derived from Smoking Timeline Follow Back interview (i.e., achieving ≥ 24 hr abstinence, days to lapse, days from lapse to relapse; C.7), (b) The 29-item Inventory of Depressive and Anxious Symptomatology¹⁹⁶ Social Anxiety, General Depression, Traumatic Intrusions subscales; (c) 18-item Adult Self-Report Scale for ADHD¹⁹⁷ adapted for past-week symptom assessment; (d) SHAPS anhedonia scale,¹⁸⁰ (e) objective body weight via a medical-grade scale; (d) adiposity via bioimpedance monitor (InBody520, GE Healthcare)—a non-invasive 2-min scan that analyzes body electrolytes to yield fat, muscle, and water composition estimates, which we will use to generate percent body fat outcomes. In addition to self-reports of medication adherence, detectable bupropion, >5 ng/mL in urine¹⁹⁸ during study visits will be used as a supplemental marker. Though participants will be told to avoid use of other quit treatments, e-cigarettes, or tobacco/nicotine

products during the trial, these will still be assessed via self-report and participants who report transitioning to e-cigarettes will be analyzed as an exploratory intermediate outcome.

C.7 Analytic Plan

Preliminary Analyses. Distributions will be examined to determine the need for normalizing transformations. Using ANOVA or X^2 test, we will examine if groups differ at pretreatment on relevant variables (despite randomization) to inform possible inclusion in analyses.

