Primary Aim 1: Smoking Outcome. 7-Day biochemically-verified PPA (missing coded as smoking) at 4- 8- 16- and 26-week post-quit follow-up will be evaluated using individual latent growth curve models (LGCM) for longitudinal binary outcomes including planned covariates (FTND, sex, SHAPS anhedonia score, BMI), the main effects of medication (BUP-450 vs. BUP-300), and the effect of time. Non-linear effects of time will be explored using nested likelihood ratio tests prior to evaluating hypotheses. Treatment by time interactions will be examined to characterize medication effects before and after treatment termination. To understand at what stage of the cessation process the treatments exert their effects, we will also analyze cessation milestone outcomes of attaining abstinence (yes vs. no abstinent for >24hr in the first 2 weeks post-quit), days to lapse (i.e., first puff), and days from lapse to relapse (i.e., first puff until the onset of 7 consecutive days of smoking) using logistic and cox regression. Sensitivity analyses of treatment effects will examine medication adherence and counseling visit attendance as moderator of treatment effects and we will re-analyze primary models in the subset of fully-adherent participants. Additional comparisons of side effects between the conditions will be conducted to verify tolerability of BUP-450.

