Primary Aim 2: Mediation. Aim 2 will examine slopes from individual piece-wise LGCMs (or raw difference scores when only 2 timepoints available) to model changes in reward processing (see C.6) prior to quit day, the jump from pre to 1-week post-quit, and post-quit changes. A latent variable framework using Mplus 7.4 will allow estimates of treatments on individual growth in mediators (path 'a') to be modeled jointly with effects of growth in likelihood of abstinence (path 'b') using models that limit bias in estimates and provide accurate evaluation of mediation using bias corrected effect estimation and product of coefficients procedures. We will attempt to create a composite that amalgamates all reward processing mediators using principal component analysis (PCA), or if a strong component is not detected, test each raw variable individually. We will model time to lapse first and other smoking outcomes secondarily with and without smoking as a time-vary covariate. Additional multiple mediator models adding all 3 growth pieces simultaneously and including the discriminant constructs (negative affect, urge to smoke to alleviate negative affect) will be test the specificity of effects.

Secondary Aims: Aim 3 will examine medication effects on anhedonia (SHAPS) and related psychopathology (i.e., depressive, social anxiety, ADHD, PTSD symptoms) and body weight and body fat percentage trajectories using individual growth models (intercept and slope) of assessments at visits during treatment. Moderation of the differential effect of treatment (Aim 4) will be assessed with interaction terms of treatment condition and corresponding moderators (SHAPS, depressive, social anxiety, ADHD, PTSD symptoms) in successive models as described above in LGCM.

Supplemental analyses of the biological variable of sex and other characteristics (age, ethnicity/race). Using the strategies above, we will examine if sex, ethnicity/race, and FTND moderate treatment effects on primary and secondary outcomes. We will report sex-stratified analyses and test, amongst women, whether days since menstruation at the onset of treatment and quit day moderates outcome using several classification methods (follicular vs. luteal; early follicular vs. late follicular vs. mid luteal vs. other).

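### Aim 3 limits the weight and symptom models to visits during treatment, so whether a benefit of BUP-450 lasts or reverses after the drug stops has no pre-specified analysis

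*Combined protocol and SAP*

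**What the plan says.** **Aim 3 analysis (C.7, Secondary Aims).** The outcomes are SHAPS anhedonia, depressive, social anxiety, ADHD and PTSD symptoms, and "body weight and body fat percentage trajectories using individual growth models (intercept and slope) of assessments at visits during treatment". Aim 3 in the Specific Aims carries no on-treatment limit.

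**Measurement (C.6).** The list is headed "Outcome assessments (Baseline, 4-wk, 8-wk, 16-wk, 26-wk", and the symptom scales, SHAPS, weight and adiposity all fall under it. C.5 adds that weight is monitored at each study visit.

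**Dosing (C.5, Medication).** BUP-450 has an "8-week post-quit treatment period (3 x 150 mg tablets), and 1-week down-titration (2 x 150 mg tablet". The BUP-300 arm differs only in the pre-quit run-in and the 8-week period, so both arms take 300 mg in the down-titration week. The randomised dose difference ends at week 8 and drug ends at about week 9.

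**Visit count (C.5, Schedule).** There are 7 in-treatment and 3 post-treatment visits.

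**Aim 1, for contrast (C.7).** "Treatment by time interactions will be examined to characterize medication effects before and after treatment termination". Aim 3 has no counterpart.

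**Intended use.** A.10 reports that the standard dose limited weight gain relative to placebo and varenicline, "though effects were modest and not robust at long-term follow-up". A.11 says that if BUP-450 does not raise quit rates but "improves weight gain and/or mental health without additional side effects, the trial would still provide invaluable evidence of a new cessation treatment".

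**The concern.** A model fitted only to readings taken on drug gives the same answer whether the arm difference later persists, halves or vanishes. It cannot distinguish weight gain prevented from weight gain postponed until the tablets stop, and the same holds for symptoms. A.11 treats a weight or mental-health benefit as enough to favour BUP-450 without a quit-rate advantage. As planned, that conclusion would rest on on-drug readings, and any week-16 or week-26 result for these outcomes would be post hoc.

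A second difficulty is that C.7 does not define which visits are during treatment. The answer decides how many symptom readings the intercept-and-slope model has.

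**Working it through.** **1. Is there another analysis of the week-16 and week-26 readings?** Aim 1 concerns abstinence. Aim 2 concerns mediators of smoking outcomes. Aim 4 tests baseline moderators of the cessation outcome. The supplemental sex, race and FTND analyses do cover secondary outcomes, but reuse the strategies already set out and so add no time window. None of them analyses these readings.

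**2. Which visits are in treatment?** The Table columns -4, -2, -1, 0, 1, 2 and 4 make 7; weeks 8, 16 and 26 make 3. By that count week 8 is follow-up, although full dose runs up to it. The symptom scales would then have only baseline and week 4. Per arm, for an intercept-and-slope model:

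- Two readings: 2 means + 3 (co)variances = 5 moments, against 2 factor means + 3 factor (co)variances + 1 residual variance = 6 parameters. Not identified.
- Baseline, 4 and 8: 3 + 6 = 9 moments, against 2 + 3 + 3 = 8 parameters. Identified.
- All five readings with two slopes joined at week 8: 5 + 15 = 20 moments, against 3 + 6 + 5 = 14 parameters. Identified.

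Weight may have a longer on-treatment series, since it is monitored at each visit, though some visits can be by phone. For body fat, the Table footnote "Body adiposity scan" is attached only to the screening and week-8 marks, while C.6 lists five times. If two scans are right, the two-reading count applies. C.7 allows a fallback, "or raw difference scores when only 2 timepoints available", only under Aim 2.

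**3. The plan's own figure.** C.8 states power above .80 for these outcomes at d above 0.3. It gives no time points, correlations or scale for d, so the figure cannot be reproduced. The nearest check is a two-group comparison of means at 0.3 SD, two-sided .05 (sidedness is assumed): power .642, .738 and .827 with 120, 150 and 187 per arm. A longitudinal model could do better. The finding does not depend on this figure.

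**4. What can be estimated.** Take an arm-difference model with one slope to week 8 and another after it. Fitted to weeks -4, 4 and 8 (baseline placed at week -4), its design matrix has rank 2 of 3, so the off-drug slope is not estimable. Adding weeks 16 and 26 gives rank 3 of 3.

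**5. Precision, change from baseline to week 26.** With 0.3 in SDs of the analysed change (an assumption), SE = sqrt(4/N). The lower N is 0.813 × 300 = 244, using the share completing all follow-ups in the prior trial cited in C.4.

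| | N = 300 | N = 244 |
|---|---|---|
| SE | 0.115 | 0.128 |
| 95% half-width (SD) | 0.226 | 0.251 |
| Power if 0.3 persists | .738 | .649 |
| Power if 0.15 persists | .255 | .216 |

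**6. Precision, change from week 8 to week 26.** Assume compound symmetry, 150 per arm, no dropout, and a 0.3 SD difference at week 8 (SD of a single reading) that falls linearly to zero at week 26. The slope difference is 0.3/18 = 0.0167 per week, and the contrast is 18 times the slope.

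| Within-person correlation | SE of slope | SE of contrast (× 18) | Power, full loss |
|---|---|---|---|
| 0.5 | 0.00594 | 0.107 | .80 |
| 0.7 | 0.00460 | 0.083 | .95 |
| 0.85 | 0.00325 | 0.059 | above .99 |

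If only half is lost (0.15), power is Φ(0.15/SE − 1.96): about .29, .44 and .73. Dropout would lower all of these.

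**The case against.** The strongest defence is that an on-treatment test is a legitimate lead analysis for a secondary aim, and that the phrase limiting the visits may be loose drafting. That the visit count leaves the symptom scales with too few readings supports this. It stands as an explanation, but the written rule still excludes the later readings and nothing replaces it.

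Several stronger readings are tempting and should be resisted:

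- *That rebound cannot be seen.* Weight and symptoms are scheduled at weeks 16 and 26 and can be reported. What is absent is pre-specification.
- *That the in-treatment set is baseline, 4 and 8.* The plan never says so; the visit count points elsewhere, and weight may have more readings.
- *That A.10 makes follow-up the place where the higher dose must prove itself.* A.10 compares 300 mg with placebo and varenicline, not 450 with 300 mg. It is a reason to look, not evidence of fading.
- *That extra quitters on BUP-450 make the off-drug weeks specially vulnerable.* The abstinence gaps assumed in C.8 are 45 − 30 = 15 points at week 4, 38 − 25 = 13 at week 8, and 30 − 20 = 10 at weeks 16 and 26, so the imbalance is larger on treatment.
- *That the Table settles the scan schedule.* Some of its marks disagree with the text as reproduced, so the conflict with C.6 needs resolving, not assuming.

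**Conclusion.** The concern holds as a gap in pre-specification. The week-16 and week-26 readings of the Aim 3 outcomes have no planned analysis, so the trial has no planned test of whether an on-drug weight or symptom benefit persists or reverses, although A.11 would build a case for BUP-450 on such a benefit. The on-treatment comparison remains valid and no loss of stated power is claimed.

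In size, 2 of the 4 post-baseline outcome assessments in C.6 and the 18 weeks from week 8 to week 26 (the first being down-titration) fall outside the planned models; 3 of 4 assessments do if week 8 counts as follow-up. The off-drug slope cannot be estimated without these readings and can be with them. The precision figures rest on the assumed effect scale, correlation structure and retention shown above.

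A reader might infer that a week-26 interval covering zero would show the benefit does not last. It would not: if the whole 0.3 SD persisted, the result would still be non-significant about 26% to 35% of the time (1 − .738, 1 − .649). Nor would either added contrast separate drug withdrawal from weight gain due to quitting; both estimate the randomised difference as a whole.

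**What to change.** 1. Define the in-treatment visits, count week 8 as the end-of-treatment reading, and keep the on-treatment slope as the lead Aim 3 test.
2. For weight and symptom scores, extend the model to weeks 16 and 26 with a second slope from week 8; C.7 already uses piece-wise growth models in Aim 2. Pre-specify two supportive contrasts per outcome, each with a 95% CI: the arm difference in change from week 8 to week 26 (rebound) and from baseline to week 26 (net durable effect).
3. Describe any Aim 3 benefit as on-treatment and report the week-26 estimate and interval beside it, without reading non-significance as lack of durability.
4. Reconcile the adiposity scan times in the Table and C.6. If only two scans are taken, analyse body fat as baseline-adjusted change at week 8. If all five are taken, treat it like weight.

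**Cost.** Weight and questionnaires need no new visit or measure. There are 2 × 6 = 12 more supportive contrasts, or 2 × 7 = 14 if body fat has off-drug scans. Week 26 will have more missing data, and power there is about .65 to .74 at 0.3 SD. An off-drug statement about body fat needs a scan at week 26. If that is not already planned, it adds two minutes per person at an existing visit, at most 300 × 2 = 600 minutes (10 hours) in all.

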Bupropion is an anti-depressant that increases striatal dopamine transmission,¹⁰ improves reward processing¹⁰ and is widely available at a modest cost.¹¹ The standard 300 mg/day dose of bupropion has demonstrated clear efficacy for smoking cessation in various populations.^{12,13} Outside of the smoking literature, high dose bupropion (400-450 mg/day) exhibits superior efficacy relative to the 300 mg/day dose for treating psychiatric disorders,^{14,15} reducing weight and body fat,¹⁶ and alleviating anhedonia,¹⁴ without meaningfully increasing side effects.¹⁷ Thus, high dose bupropion may be particularly effective at promoting smoking cessation in anhedonic smokers, improving anhedonia-related mental health, and preventing post-quit weight gain. To the best of our knowledge, 300 mg/day is the highest bupropion dose tested for smoking cessation in any population to date.

In this continuation proposal, we translate work in the prior period on mechanisms underlying relapse in anhedonic smokers to the development of a novel, disseminable, and putatively effective treatment for this high risk population. We propose a clinical trial in which anhedonic smokers are provided standard cessation counseling and randomized to either: the standard 300 mg/day dose of bupropion (BUP-300; N=150) or a high 450 mg/day dose (BUP-450; N=150). In addition to treatment effects on 7-day point prevalence smoking abstinence (PPA) outcomes, we will: i) examine if improvement in reward processing is a mechanism of action for BUP-450's efficacy with innovative laboratory-based computer task and subjective indices of reward processing, ii) assess moderators of treatment efficacy, iii) investigate treatment effects on secondary mental health and body weight and adiposity outcomes; and iv) utilize the extended release (XL) formulation that requires dosing only once per day, which has yet to be tested for cessation and may increase adherence.

Primary Aims

- 1. To test the efficacy of high dose bupropion for smoking cessation in anhedonic smokers.** Hyp 1. PPA rates across the 6-month post-quit follow-up period will be higher in BUP-450 vs. BUP-300.

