Recruitment and timeline. We plan 3 months for startup, 9-months for an initial pilot, 31 months for primary trial accrual, 8 further months to complete data collection and follow-ups, and 9 months for analysis and write-up. A pilot study will be done on a subset of participants (randomize N=15 per condition) to refine procedures. The pilot will utilize the same design as the standard trial, with non-essential assessments being abbreviated for logistical purposes. Based on prior work and the efficient phone screening methods,³ we expect 16% to be ineligible at the in-person screening and 13% of consenting subjects to not complete all pre-randomization visits and be replaced. Conservatively estimating 80% eligibility and 85% randomization, 14 second-stage screens per month are needed to obtain the intent-to-treat sample of 300 randomized smokers, which had been obtained our prior 5-year trial³ using the recruitment strategies proposed here. The study will be announced via online, print, and mass media advertisements in the greater Los Angeles metropolitan area. Targeted recruitment will take place through: (1) existing research databases from USC-HEAL and [name] (Co-I; UCLA) Laboratory, which contain contact information for 2000+ daily smokers in the LA metro who wished to be called about future studies; (2) referrals from USC primary care clinics run by [name] (Co-I) and his colleagues; and (3) participants responding to advertisements to other USC-HEAL studies that are eligible for this trial.

Eligibility criteria. Inclusion: (1) Lifetime anhedonia on the PHQ-2; (2) smoking 10+ cig/day for 2+ years; (3) Aged 21-65 (21 is legal age to purchase tobacco in CA); (4) breath carbon monoxide (CO) \geq 10 ppm Exclusion: (a) past year moderate or severe DSM-IV non-tobacco substance use disorder (4+ symptoms); (b) a conservative definition of drug contraindications based on lifetime history of panic, bipolar, psychosis, bulimia nervosa, anorexia nervosa, seizure disorders, suicidal attempt (b) report of past 90-day suicidal ideation and alco-

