relapse curves in anhedonic smokers, BUP-450 vs. BUP-300 vs. PLA effects on weight loss and mental health.^{22,97,162} We generated 1,000 multivariate normal random samples of correlated binary outcomes using covariance estimates from prior trial data (range 0.55-0.25)³ and analyzed the datasets using LGCM focusing on the proportion of significant ($p < 0.05$) values for each pair-wise contrast (Aim 1). The percentage of datasets with significant effects for each hypothesis (i.e., $>80\%$ of $ps < .05$) provided a simulation-based estimate of power. Using this technique, we found that enrolling a sample size of 375 (BUP-450: $N < 150$, BUP-300 $N < 150$) conservatively would have power >0.83 to detect main effects when testing our primary hypothesis, allowing for 20% attrition among those enrolled. Parallel simulations were conducted using LGCM to assess power for growth trajectories in continuously scaled mediators assuming an effect of treatment dose response on reward processing ($ds > 0.3$), and reward processing on outcome ($ds > 0.17$) based on the prior literature.^{131,140,201,202} We also found support for power >0.81 with average effects of 0.31 ($sd = 0.11$) with $N = 375$. Additional simulations for secondary mental health and body/weight adiposity outcomes based effects in prior literature ($ds > 0.3$)^{22,97,162} yielded adequate power ($> .80$). Missing individuals will be presumed to have continued smoking. All analyses will use an intent-to-treat approach.

REFERENCES

4. [name] AM, Zvolensky MJ. Anxiety, depression, and cigarette smoking: A transdiagnostic vulnerability framework to understanding emotion-smoking comorbidity. *Psychological bulletin*. 2015;141(1):176.
5. Gorwood P. Neurobiological mechanisms of anhedonia. *Dialogues Clin Neurosci*. 2008;10(3):291-299.

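### Aim 3 does not commit its growth models to using the pre-randomization score; if baseline is left out, or the arms are left free at the intercept, the test is valid but less precise than it need be

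*Combined protocol and SAP*

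**What the plan says.** C.7 gives Aim 3 a single sentence. Treatment effects on SHAPS, the related psychopathology scales, weight and percent body fat are to be examined "using individual growth models (intercept and slope) of assessments at visits during treatment". The sentence does not say:

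- whether the pre-randomization score is a response, a covariate or omitted;
- which growth terms carry an arm effect;
- which contrast is the test.

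C.6 sets the measurement times: "Outcome assessments (Baseline, 4-wk, 8-wk, 16-wk, 26-wk"). Baseline precedes treatment. Of the later times, weeks 16 and 26 follow treatment, so weeks 4 and 8 are the in-treatment ones.

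C.8 reports power for these outcomes in one sentence: "Additional simulations for secondary mental health and body/weight adiposity outcomes based effects in prior literature", with effects of d above 0.3, which "yielded adequate power ($> .80").

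**The concern.** Two readings of the sentence come naturally, and each gives up precision.

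- **Baseline as first occasion, arm effects on both intercept and slope.** The arm effect on the intercept is then a baseline difference, which randomization makes zero in expectation. Estimating it turns the slope test into something close to a change-score comparison.
- **In-treatment visits only.** Baseline drops out. A week-8 comparison is then unadjusted. A slope contrast sees only the change from week 4 to week 8 and misses any benefit already present at week 4.

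What is at stake is the sensitivity of the secondary outcomes. A.11 leans on them: if the higher dose does not improve quitting, a mental health or weight benefit is what would still make the trial informative.

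**Working it through.** **Inputs**

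- Arm size: 150. Specific Aims has participants "randomized to either: the standard 300 mg/day dose of bupropion (BUP-300; N=150) or a high 450 mg/day dose (BUP-450; N=150"), and C.4 plans to "obtain the intent-to-treat sample of 300 randomized smokers".
- Alpha: 0.05, from C.8 ("focusing on the proportion of significant ($p < 0.05$) values"). That phrase concerns Aim 1 and does not state sidedness; two-sided is assumed.
- Effect: 0.3 SD at week 8, from C.8's lower bound ("based effects in prior literature ($ds > 0.3"). C.8 does not define the standardizer; the cross-sectional SD is assumed.
- Times from start of treatment: 0, 8 and 12 weeks for baseline, week 4 and week 8, given the 4-week run-in.
- Path: 0.2 SD at week 4 and 0.3 SD at week 8, a straight line of 0.2/8 = 0.3/12 = 0.025 SD per week (assumed).
- Correlation rho between visits: not given for symptom scores. C.8's range of 0.25 to 0.55 is for the binary abstinence outcome. Assumed 0.4 to 0.7, equal for every pair of visits (compound symmetry).
- No drop-out.

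Power is Phi(effect/SE − 1.96).

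**Step 1. The plan's own figure.** For an unadjusted single-visit comparison SE = sqrt(2/n).

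- 150 per arm: SE 0.1155, power 0.738.
- 375/2 = 187.5 per arm: power 0.828.
- 150 × 0.8 = 120 per arm: power 0.642.

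C.8 gives neither the N, the correlations nor the contrast for these outcomes, so its figure of above .80 can be neither reproduced nor refuted.

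**Step 2. Week 8 alone.** With baseline as covariate, SE = sqrt(2(1 − rho²)/n). At rho = 0.5 this is sqrt(2 × 0.75/150) = 0.1000, and power is Phi(3.00 − 1.96) = 0.851. Without baseline it is 0.738, a loss of 0.113.

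**Step 3. Three-visit slope test.** The times have mean 20/3 and sum of squares about the mean 208 − 400/3 = 74.67.

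- Arms free at the intercept: SE = sqrt(2(1 − rho)/(n × 74.67)). At rho = 0.5 this is 0.00945; 0.025/0.00945 = 2.65; power 0.754.
- Common baseline mean: SE = sqrt(2(1 − rho)/(n × [208 − 400 rho/(1 + 2 rho)])). At rho = 0.5 the bracket is 108; SE 0.00786; 0.025/0.00786 = 3.18; power 0.889.

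**Step 4. Over the assumed correlations, 150 per arm** (losses taken before rounding):

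| rho | Slope, arms free | Slope, common baseline | Loss | Week 8, no baseline | Week 8, adjusted | Loss |
|---|---|---|---|---|---|---|
| 0.4 | 0.676 | 0.862 | 0.187 | 0.738 | 0.809 | 0.071 |
| 0.5 | 0.754 | 0.889 | 0.136 | 0.738 | 0.851 | 0.113 |
| 0.6 | 0.841 | 0.926 | 0.085 | 0.738 | 0.901 | 0.163 |
| 0.7 | 0.927 | 0.965 | 0.038 | 0.738 | 0.953 | 0.215 |

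The two losses move in opposite directions as rho rises.

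**Step 5. Baseline excluded, slope from week 4 to week 8.** The arm difference in change is 0.3 − 0.2 = 0.1 SD, with SE = sqrt(4(1 − rho)/n). At rho = 0.5, SE is 0.1155 and power is 0.137. Over rho 0.4 to 0.7 it is 0.12 to 0.20. An effect of 0.3 SD at both visits gives a slope difference of zero and a rejection rate of 0.05.

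**Step 6. Body weight.** At an assumed rho of 0.95, the week-8 change-score SE is sqrt(4 × 0.05/150) = 0.0365, against an adjusted SE of sqrt(2 × 0.0975/150) = 0.0361. Where baseline is already modelled there is almost nothing to gain. If baseline is excluded, power at 0.3 SD remains 0.738.

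**The case against.** The strongest reply is that C.7 is silent, not wrong. Naming an intercept and a slope lists growth terms; it does not say that arm acts on both. A model with the arm effect on the slope alone, which is the common-baseline model, fits the same words. A reader might infer that the plan has decided to discard baseline adjustment. The documents do not support that.

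Other passages also bear on baseline. C.7's preliminary analyses check for pretreatment differences that may lead to covariates. C.5 balances SHAPS and BMI through the urn. Aim 1 names both as planned covariates. The missing-data paragraph adds predictors of missingness to the models. And a free-intercept growth model is a valid, standard analysis of a randomized comparison: no bias or inflated type I error is shown.

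Most of this stands, but it does not close the gap. Adding a covariate because an imbalance test flagged it is data-driven, and the precision gain does not depend on observed imbalance. The urn does not cover the depressive, social anxiety, ADHD or PTSD scores, and balancing a factor without modelling it does not deliver the gain. The named covariates belong to Aim 1. Nothing commits Aim 3 to adjustment, and nothing rules it out.

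**Conclusion.** The point holds as a matter of efficiency in the secondary outcomes. Aim 3 leaves open whether an already collected baseline score is used, and both natural readings give a weaker test than adjustment would. At 0.3 SD, 150 per arm, two-sided 0.05, correlation 0.5 and no drop-out, power is about 0.74 to 0.75 against 0.85 to 0.89.

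No single loss belongs to the plan. The size depends on a correlation that the documents do not give and on which reading is taken. The most damaging reading is the one that excludes baseline and tests only the week 4 to week 8 slope.

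A reader might also infer that C.8's claim of power above .80 fails. That is not shown. Its N and correlations are unstated; at 187.5 per arm even the unadjusted week-8 comparison reaches 0.828, and at 150 per arm with correlation 0.6 the free-intercept slope test reaches 0.841. How 375 relates to 150 per arm is a separate question.

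**What to change.** Amend the Aim 3 sentence in C.7 to state that:

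- the pre-randomization score enters every Aim 3 model, either as a covariate or as the first response with one mean common to both arms;
- the arm effect is tested only on the post-baseline treatment visits, with those visits listed;
- the contrast is named, for example the week-8 difference between arms.

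Adjustment should not depend on whether the arms happen to differ at pretreatment. The cost is analytic-plan wording only: the data and software stay the same.
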